# 3.3.2.2.1 Neutropenia

In the lead-in stage, subjects will not receive growth factors prior to C1D1 and prophylactic use of growth factors is prohibited during the first 3 cycles (Days 1-84) or until neutropenia is identified as a DLT (at discretion of the Principal Investigator or designee), whichever comes first. Growth factors can be used during a drug hold to assist the recovery and in subsequent cycles after a drug hold. Please note that G-CSF should not be used within at least 24 hours of the last dose of CRLX101 treatment.

In the Phase 2 stage, subjects may receive growth factors prophylactically at the discretion of the Principal Investigator or designee.

# 3.3.2.2.2 Thrombocytopenia

Thrombocytopenia will be treated conservatively. In the absence of bleeding or a necessary invasive procedure, platelet transfusions should be given for a platelet count  $\leq 10,000/mcL$ . If invasive procedure(s) is (are) planned, or the participant develops bleeding, platelet transfusions should be administered in accordance with the standard of practice, usually maintaining a platelet count above 50,000/mcL

# 3.3.2.2.3 Anemia

Symptomatic anemia should be treated with red blood cell transfusion and is recommended if the hemoglobin falls below 8 g/dL or the participant is symptomatic. Erythropoietin (EPO) may also be given per clinical guidelines.

# 3.3.2.3 CRLX101-Related Non-Hematologic Adverse Events

Table 4: Dose Modification and Management of Non-Hematologic Adverse Events (CRLX101)

Observation	Action
Grade 1 or 2 AEs resolves promptly (within 48 hours) with supportive care	Maintain dose level (DL)
Any $\geq$ 3 non-hematologic*	Hold study drug(s) causing the toxicity for up to 28 days until toxicity resolves to $\leq$ Grade 1. Treatment with CRLX101 may be restarted at one DL lower, as per the dose reduction guidelines.
	Lab abnormalities that can be readily corrected (e.g. electrolyte abnormalities) do not require a dose reduction unless by discretion of the PI or designee.
Grade 3 or 4 non-hematologic AE related to drugs that does not	Remove participant from CRLX101 therapy.

Observation	Action
resolve to grade 1 or less within 28 days despite maximum supportive care after treating participant at the lowest reduced DL	
Toxicities requiring more than 2 dose reductions	Remove participant from CRLX101 therapy.

\* Except fatigue/asthenia < 2 weeks in duration; mucositis in subjects who have not received optimal therapy for mucositis; vomiting or diarrhea lasting less than 72 hours whether treated with an optimal anti-emetic or anti-diarrheal regimen or not; or alkaline phosphatase changes

3.3.2.4 Management of the hypersensitivity/infusion reactions

Table 5: Dosing modification and management of hypersensitivity reactions (CRLX101)

Grade 1 or 2	Stop infusion immediately, continue hydration fluids and provide medications as indicated per institutional guidelines			
	If symptoms resolve within 1-2 hours, at Principal Investigator or designee's discretion may re-start study drug administration at slower rate (i.e. 2x slower rate) and increase rate slowly to complete administration of full dose			
	OR			
	Hold dose administration on day of event, and resume treatment at next scheduled day at the slower rate.			
	Additionally, if an HSR occurs upon re-administration at the slower infusion rate, the participant will be removed from study.			
Grade 3 or 4	Stop infusion immediately and administer medical support as indicated per institutional guidelines.			
	Hold dose administration on day of event			
	Review with study Principal Investigator or designee to determine whether to discontinue from study drug treatment. Confirm that rate of administration was appropriate and pre-meds were given as suggested.			

If opting to resume CRLX101 infusion following Grade 1 or 2 HSR, administration of CRLX101 should be over 120 minutes (+/- 10 minutes) (using the following infusion schedule) with additional pre-medications (dexamethasone 20 mg PO or IV, famotidine 20 mg IV or PO, acetaminophen 650 mg PO, ondansetron 16 mg PO or IV, and diphenhydramine 50 mg PO or IV).

CRLX101 in 500 mL 5% dextrose IV infusion:

- 15 mL/hr for 15 minutes, then increase to
- 30 mL/hr for 15 minutes, then increase to
- 60 mL/hr for 15 minutes, then increase to
- 120 mL/hr for 15 minutes, then increase to
- 240 mL/hr for 15 minutes, then increase to
- 480 mL/hr for 15 minutes, then increase to
- 528 mL/hr for 30 minutes to complete infusion

Please note: a gradual increase in rate may be used in place of incremental rate increases. Infusion rates may also be adjusted at the discretion of the investigator.

If a subject has a history of infusion related reactions to other drug treatments, or has many environmental allergies (e.g. food, pollen), the total infusion time may be slowed during the first CRLX101 infusion and for all subsequent infusions, at the discretion of the Principal Investigator or designee.

# 3.3.3 Enzalutamide Dose Modification

If a participant experiences  $a \ge Grade 3$  non-hematologic toxicity (except hypertension) attributable to enzalutamide, withhold dosing for up to 1 month or until symptoms improve to  $\le$  Grade 2, then resume at the same dose if clinically appropriate. If toxicity recurs and/or in the judgment of the investigator dose reduction is appropriate, lower dose levels (120 mg/DL-1 or 80 mg/DL-2), may be considered. Enzalutamide may be discontinued if toxicity recurs and dose modification is no longer clinically appropriate.

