- 2.1.2.3 Patients with known brain metastases should be excluded from this clinical trial because of their poor prognosis and because they often develop progressive neurologic dysfunction that would confound the evaluation of neurologic and other adverse events.
- 2.1.2.4 Patients with a recent (within 1 year) history of seizure or any condition that, in the opinion of the investigator, significantly increases seizure risk. Also current or prior treatment with anti-epileptic medications for the treatment of seizures. Transient ischemic attack within 12 months prior to study enrollment will not be permitted.
- 2.1.2.5 History of allergic reactions attributed to compounds of similar chemical or biologic composition to enzalutamide, CRLX101, or other agents used in study.
- 2.1.2.6 Patients with a history within the last 3 years of another invasive malignancy (localized non-melanoma skin and bladder cancers are allowed).
- 2.1.2.7 Uncontrolled intercurrent illness including, but not limited to, ongoing or active infection, symptomatic congestive heart failure, unstable angina pectoris, cardiac

arrhythmia, uncontrolled hypertension (SBP>170/DBP>105), or psychiatric illness/social situations within 6 months that would limit compliance with study requirements.

- 2.1.2.8 Patients who have received palliative radiotherapy within 2 weeks of study entry and have not recovered to Grade 1 or baseline from associated toxicities. Note: Patients may receive palliative radiation once enrolled on study, as per guidance outline in Section **4.2.2**. The subject has not recovered to baseline or CTCAE  $\leq$  Grade 1 from toxicity due to all prior therapies, including surgery, except alopecia and other non-clinically significant AEs.
- 2.1.2.9 Patients who are unable to swallow tablets or have a gastrointestinal disease that could hinder the absorption of enzalutamide
- 2.1.2.10 The use of any herbal products that may lower PSA levels (e.g. saw palmetto).
- 2.1.2.11 Patients with microscopic hematuria (defined as >100 RBCs on urinalysis) or worsening urinary symptoms within 7 days prior to the initiation of study treatment.

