Weekly differential blood counts including reticulocytes (calculate reticulocyte index (RI), RI = reticulocyte count x hematocrit (Hct)/normal Hct; a value of 45 is usually used for normal Hct) and peripheral blood smear could be considered (may be done at an outside facility). If any blood parameters remain clinically abnormal after 4 weeks further investigations could be considered including hematology evaluation. Bone marrow analysis and/or blood cytogenic analysis could be considered at this stage according to standard hematological practice.

Development of a confirmed myelodysplastic syndrome or other clonal blood disorder should be reported as an SAE. Study treatment should be discontinued if diagnosis of myelodysplastic syndrome is confirmed.

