# 3.6.1 Criteria for removal from protocol therapy

- Progressive disease
- Participant requests to be withdrawn from active therapy
- Unacceptable toxicity as defined in Section 3.3
- Toxicity related dose delay lasting longer than 28 days in which case participant will be removed from the drug causing the toxicity
- Investigator discretion
- Requirement for any drug deemed to cause an significant drug-drug interaction that could impact the study treatment (at discretion of the PI and/or Associate Investigator and as discussed in Section 4.1)

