## 14.2.2 Toxicity

## Seizures

In the randomized clinical trial, 7 of 800 (0.9%) participants treated with enzalutamide 160 mg once daily experienced a seizure. No seizures occurred in participants treated with placebo. Seizures occurred from 31 to 603 days after initiation of enzalutamide. Participants experiencing seizure were permanently discontinued from therapy and all seizures resolved. There is no clinical trial experience re-administering enzalutamide to participants who experienced seizures. The safety of enzalutamide in participants with predisposing factors for seizure is not known because these participants were excluded from the trial. These exclusion criteria included a history of seizure, underlying brain injury with loss of consciousness, transient ischemic attack within the past 12 months, cerebral vascular accident, brain metastases, brain arteriovenous malformation or the use of concomitant medications that may lower the seizure threshold. Because of the risk of seizure associated with enzalutamide use, participants should be advised of the risk of engaging in any activity where sudden loss of consciousness could cause serious harm to themselves or others.

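### Section 3.3.3, the only enzalutamide-specific toxicity dose rule, makes no exception for seizure: it allows hold-and-resume at Grade 3 or higher, requires no hold below that, and never itself requires stopping

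*Combined protocol and SAP*

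**What the plan says.** Section 3.3.3 applies to a Grade 3 or higher non-hematologic toxicity attributed to enzalutamide, with hypertension the only exception. Dosing is withheld for up to 1 month or until the toxicity is Grade 2 or lower, "then resume at the same dose if clinically appropriate". If the toxicity recurs, and/or "in the judgment of the investigator dose reduction is appropriate, lower dose levels" of 120 or 80 mg may be considered. On stopping, the section says: "Enzalutamide may be discontinued if toxicity recurs and dose modification is no longer clinically appropriate". Seizure is not named there or anywhere else in Section 3.3.

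Seizure does appear elsewhere:

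- **Exclusion criterion 2.1.2.4** keeps out "Patients with a recent (within 1 year) history of seizure", other conditions that raise seizure risk, and current or prior anti-epileptic treatment for seizures.
- **Sections 4 and 4.1.1** advise caution with drugs that lower the seizure threshold.
- **Section 14.2.2**, describing the earlier randomized trial, says: "Participants experiencing seizure were permanently discontinued from therapy and all seizures resolved". It adds: "There is no clinical trial experience re-administering enzalutamide to participants who experienced seizures".

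Some general provisions also reach enzalutamide. Section 3.3.1 allows at most two dose reductions, with no re-escalation, and lets a participant continue one agent if the other is stopped for toxicity. Section 3.6.1 lists unacceptable toxicity as defined in Section 3.3, investigator discretion, and this: "Toxicity related dose delay lasting longer than 28 days in which case participant will be removed from the drug causing the toxicity".

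**The concern.** Section 3.3.3 treats a seizure like any other non-hematologic toxicity. As written, it leaves open giving enzalutamide again, at full dose and within about a month, to someone who has just had a seizure attributed to it. That person would fail the trial's own entry criterion. The protocol also says there is no trial experience of re-administration, so the judgment of what is clinically appropriate has no such experience to guide it.

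What is at stake is the safety of an individual participant. The primary endpoint, the two-stage design and the error rates are unaffected.

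**Working it through.** **1. What each text requires after an on-study seizure attributed to enzalutamide**

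| Provision | Grade 3 or higher | Below Grade 3 | Is stopping required? |
|---|---|---|---|
| 3.3.3 | Hold, then resume if appropriate | No hold required | No; optional, after recurrence |
| 3.3.3.1 | Covers missed appointments only | Same | No |
| 4.1.2 (80 mg rule) | Covers a drug interaction only | Same | No |
| 3.6.1, delay over 28 days | Only if the delay lasts that long | Same | Yes, but a quickly resolving seizure need not reach it |
| 3.6.1, unacceptable toxicity | Refers back to Section 3.3 | Same | Section 3.3 never names seizure |
| 3.6.1, investigator discretion | Permits removal | Permits removal | No |
| 14.2.2 | Reports practice in another trial | Same | No; it is background |

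No row requires enzalutamide to stop because a seizure occurred. A seizure that settles in a few days meets the improvement limb of 3.3.3 well before 28 days.

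**2. Event-specific stops elsewhere.** For a confirmed marrow disorder, Section 3.3.2.2 says: "Study treatment should be discontinued if diagnosis of myelodysplastic syndrome is confirmed". Table 5 removes a participant whose hypersensitivity reaction recurs at the slower infusion rate. A seizure stop would therefore fit the protocol's existing form.

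**3. Expected number of seizures**

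Inputs: 7 seizures in 800 on enzalutamide (14.2.2); accrual ceiling 30, lead-in of 3 to 6 and stage 1 of 8 (10.2).

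- Rate: 7/800 = 0.00875, or 0.875%, which reproduces the stated 0.9%. The exact (Clopper-Pearson) 95% interval is 0.00352 to 0.01794.
- At the ceiling: 30 × 0.00875 = 0.2625. At the interval limits: 30 × 0.00352 = 0.106 and 30 × 0.01794 = 0.538.
- If the trial stops after stage 1, with 3 + 8 = 11 to 6 + 8 = 14 participants: 11 × 0.00875 = 0.096 and 14 × 0.00875 = 0.1225.
- Chance of at least one seizure among 30: 1 − (1 − 0.00875)^30 = 0.232.

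**4. Scaling for shorter exposure (an assumption)**

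Suppose risk is proportional to time on drug, and time on drug follows median time to progression. Section 1.2.2 gives 8.3 months for the 800-patient enzalutamide arm, taken here to be the source of the 7/800. Section 10.2 gives 4 to 5 months for the later-line cohorts.

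- 4/8.3 = 0.482, so 0.2625 × 0.482 = 0.127.
- 5/8.3 = 0.602, so 0.2625 × 0.602 = 0.158.

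These figures count seizures of any grade and cause. Actual re-challenge would be rarer, because it also needs attribution to enzalutamide and a decision to resume. The documents give no rate for either and no split by seizure grade.

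**The case against.** The strongest reply is that 3.3.3 does not direct re-challenge. Resumption is conditional on clinical judgment, 3.6.1 lets the investigator stop at any time, and the facts needed for that judgment are in Section 14.2.2. The team discusses each participant weekly (7.4.1), and a seizure meeting the serious criteria is reported within 24 hours (8.3). This is fair, and most investigators would probably stop. Oversight does not change what the rule allows, however, and review after the event does not supply the missing experience.

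Second, Section 14.2 refers to the package insert, which might settle the matter. It is not in the documents, so this cannot be judged. The conclusion is limited to the protocol's own text, where a general pointer to agent information does not displace an explicit dose rule.

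Third, failing an entry criterion is not in itself a reason to stop. Entry needs hemoglobin of at least 9 g/dL, while Table 3 lets CRLX101 resume once anemia is Grade 2 or lower, with Grade 3 set below 8 g/dL. This stands: the entry criterion supports a firmer rule but does not prove one is needed. The comparison with myelodysplastic syndrome is likewise only supportive, since Table 5 leaves stopping after a Grade 3 or 4 hypersensitivity reaction to review with the principal investigator.

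Fourth, participants must already have had at least two cycles of enzalutamide (2.1.1.5), which with 2.1.2.4 selects people exposed without a recent seizure. Against that, the earlier trial excluded any history of seizure and the use of threshold-lowering drugs. This protocol's seizure-history exclusion covers 1 year, plus anti-epileptic treatment for seizures, and it allows threshold-lowering drugs with caution. The net effect on the rate is unknown.

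**Conclusion.** The concern holds. The omission in 3.3.3 is clear from the text, and no other provision in the protocol closes it. This is more than missing detail, because the rule as written covers seizure and permits a resumption for which the protocol reports no trial experience. That 3.3.3 never requires stopping is a statement about that section alone: the 28-day rule in 3.6.1 can force removal, but not for a seizure that resolves quickly.

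The event is uncommon. The estimate is about 0.26 seizures at full accrual (0.11 to 0.54 over the interval for the rate), about 0.10 to 0.12 if the trial ends after stage 1, and about 0.13 to 0.16 at full accrual under the exposure assumption. All of these assume the earlier trial's rate carries over. The change should be made because the possible harm is serious and the correction is cheap, not because the event is likely.

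**What to change.** Add to Section 3.3.3: *Enzalutamide will be withheld for any on-study seizure and permanently discontinued unless the seizure is clearly attributable to another cause; the hold-and-resume rule does not apply.* List the same event in Section 3.6.1 as a criterion for removal from enzalutamide. The participant may continue CRLX101 alone under 3.3.1.

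The cost is two lines in an amendment, with no added visits, tests or participants. The downside is that a rare participant loses enzalutamide, a drug on which every participant has already progressed, although the trial hopes to restore sensitivity to it. Someone whose seizure clearly had another cause need not lose it. Anyone who has had at least one dose of each agent stays in the modified intention-to-treat population of Section 10.3.

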# 3.3.3.1 Enzalutamide Dose Delay

Enzalutamide may be continued within 28 days if an appointment is missed due to scheduling or logistical issues (e.g. vacation, weather) during the treatment period. If more than 28 days have elapsed, participant will need to be seen to assess continuation of treatment procedure.

# 3.4 STUDY CALENDAR

On study assessment can be performed within  $\pm 7$  days of the specified time, unless otherwise indicated. CRLX101 can be given within  $\pm 2$  days of the specified time, unless otherwise indicated.

## Table **6:** Study Calendar

		Cycle 1		Cycle 2		Subsequent	Cycles	se vion	of ent	erm Up	
Procedure	 Screening/ Baseline	Day 1	Day 2	Day 15	Day 1	Day 15	Day 1	Day 15	 Disease Progression	 End of Treatment	 Long Term Follow-Up
History and PE	X	Х		X	X	Х	X	X	Х	Х	
Vital signs	X	Х		X	X	Х	X	X	X	Х	
ECOG Performance Score	X										
 Pathologic Confirmation of Dx	X										
 CBC/Diff	X	Х		Х	Х	Х	X	X	X		
 Acute Care Panel w/ Mineral Panel, Hepatic Panel, LDH, CK, Uric Acid, Total Protein	 X	Х		Х	X	Х	X	X	X		
 Urinalysis	 X	Х				Х					
Serum PSA	X	X		X	X	X	X	X	X		
Serum Testosterone	X	X			X		X		X		
 EKG	X	X		X	X						
Tumor Assessment: CT scan (chest, abdomen & pelvis), Tc bone scintography	X						 X		X		

		Cycle 1		Cycle 2		Subsequent Cycles		se tion	of ent	erm Up	
Procedure	 Screening/ Baseline	Day 1	Day 2	Day 15	Day 1	Day 15	Day 1	Day 15	 Disease Progression	 End of Treatment	 Long Term Follow-Up
CRLX101		Х		X	X	Х	Х	X			
Enzalutamide			X					•			
 Plasma PK		Х				Х					
 Urine PK		Х				Х					
 VEGF Biomarker, CTC, and Whole Blood Collection		X				X	 X		X		
 NanoString Sample Collection		Х				Х			X		
Adverse Events		X		X	X	Х	X	X	X	Х	
Concomitant Medications	X	X		X	X	X	X	X	X	Х	
 APTT, INR	X										
Survival Phone Call											Х

Baseline procedures are performed within 2 weeks of initiation of study therapy. Screening labs may also be used as baseline/Day 1 labs if performed within two weeks of study initiation. Height and weight must be done within 14 days of the first study dose.

To be completed on the day disease progression is noted according to PCWG3 and/or RECIST criteria. May be completed within 30 days or at end of treatment visit if logistically necessary and feasible. Subject may also be contacted by phone to assess adverse events if unwilling or unable to come to NIH."

To be completed within 30 days after the last dose of study therapy, presuming logistically feasible. The study team may contact the participant by phone to assess adverse events if unwilling or unable to come to NIH.

After the end of treatment visit the participant will receive a phone call every 6 months to assess for survival until expiration.

Pathologic confirmation should be obtained at any point prior to enrollment. If no pathological specimen is available, participants may enroll with a pathologist's report showing the histological diagnosis of prostate cancer and clinical course consistent with disease. Participant may begin therapy based on evidence of disease progression if pathologic confirmation is not available at the time of study enrollment.

Includes Neutrophils, Lymphs, Monos, Eos, Basos, WBC, RBC, Hemoglobin, Hematocrit, RBC Indices, MCV, RDW, Platelets, and RBC Indices. Results should be available prior to administration of study drugs. If absolute differentials are not available, percentage differentials are acceptable.

Acute Care Panel: Sodium (Na), Potassium (K), Chloride (Cl) Total CO2 (Bicarbonate), Creatinine, random Glucose, urea or blood urea nitrogen [BUN], eGFR; Hepatic Panel: Alkaline Phosphatase, ALT/GPT, AST/GOT, Total Bilirubin, Direct Bilirubin; Mineral Panel: Albumin, Calcium, Magnesium, Phosphorous; Lactate Dehydrogenase (LDH); Creatine Kinase (CK); Uric Acid; Total Protein;

Only the Acute Care and Hepatic panels are required at screening

Additional urinalysis will be performed as clinically indicated in the investigator's judgment.

To be done within 7 days prior enrollment/treatment.

Must be completed within 14 days prior to the first study dose of CRLX10. Please note: EKGs are required within 60-180 minutes post-infusion on C1D1, C1D15 and C2D1 of CRLX101 for participants with any conduction abnormality on baseline ECG.

Tumor Assessments will be performed prior to or on C3D1, C6D1, C9D1, and every 3rd cycle thereafter until evidence of disease progression. Primary endpoint assessment will be conducted following tumor assessment on C6D1.

See Section **5.1.1** for complete details about PK biospecimen collection time points on C1D1 and C2D15. The exact time of the draw should be recorded.

Samples are to be collected prior to treatment on the specified days. For samples collected prior to dosing on C1D1, the sample may be collected during baseline assessment or any time following baseline assessment but prior dosing on C1D1. Following disease progression, samples should be collected within 30 days, if logistically feasible.

After sample collection on C2D15, samples will be collected prior to C6D1 and at disease progression for VEGF measurement, CTC analysis, and whole blood collection.

Coagulation [activated partial thromboplastin time (APTT) and international normalized ratio (INR)] will be performed at baseline and if clinically indicated unless the participant is receiving warfarin. Participants taking warfarin may participate in this study;

however, it is recommended that prothrombin time (INR and APTT) be monitored carefully at least once per week for the first month, then monthly if the INR is stable.

